Then CPRS and administrative data will be reviewed to determine the baseline rate of patients identified at increased risk for CRC based on FHH. This rate will be compared to the rate obtained subsequent to completing MeTree so that the effectiveness for increasing the identification of higher risk patients can be determined. CPRS data abstraction will be completed by research staff at either site (Durham or Madison). Study staff at both sites (Durham and Madison) will have National Electronic Health Record (EHR) access, using VistAWeb or Joint Legacy Viewer (JLV), in order to complete these data abstractions. Medical records will be accessed using VistAWeb, JLV, or CPRS and the resulting data will be recorded in DatStat Illume, behind the VA firewall.

Blinding cannot be ensured because the MeTree decision support document for PCPs will be scanned into CPRS, and there is no practical way to prevent the RA from seeing it. At baseline, all patients enrolled in the study will have their EMR audited to determine whether they have been identified as high risk for CRC as observed by either: (1) a diagnosis of high-risk for CRC (diagnosis code: V16.0) or (2) documentation in CPRS. The RA will review progress notes from all providers for documentation of FHH of CRC, including the relationship and age at diagnosis or explicit statement of no FHH of CRC. This will be accomplished with a text search. Initially, we will validate our search terms by reading all progress notes in a subset of 25 patients. If necessary, the terms will be adjusted to accommodate those found in the progress notes, and validation will be repeated on an additional 25 patients.

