## Analyses for Aims 1-2

**Sample Size and Power Considerations.** The CRC screening rate of patients aged 50 years and older in VA is high, around 80%. However, this is based on the assumption that all patients are average-risk; as such, the risk-appropriate referral rate is not well-characterized. We estimate that the risk-appropriate CRC screening referral rate is 60% to 70%. Our final sample size calculation is based conservatively on the screening referral rate of 60%. Based on a type I error rate of 5% and Z test for the difference of two proportions adjusted for provider clustering, we will need approximately 480 patients (240 in each arm) to detect a 13% difference (i.e., 73% in the immediate arm) with 80% power. Table 1 provides

estimated differences that can be detected with this sample size for different CRC screening referral rates. Lost to follow-up either due to death or the Veteran leaving the VA system will be minimal as outcome data are collected administratively. We inflated the sample size to 500 patients to account for a 4% loss to follow-up. Patients who screen as eligible but who never log in to complete MeTree either on their own or in person will not provide data for the study and thus will not be counted toward the required sample size of 500. Thus, we may screen and consent >500 patients in order to enroll 500 who complete MeTree.

By design, patients may not be independent because they are clustered within a participating provider. The “relatedness” of patients within a PCP is measured by the intraclass correlation coefficient (ICC) and must be considered in the sample size estimation. We have a fixed number of PCPs (20 in each arm). The sample size for difference in proportions is adjusted by the intraclass correlation coefficient (ICC); we used an ICC of 0.02. Although an ICC is difficult to estimate in advance of a study, we believe this is an appropriate and conservative estimate based on our own and others’ research findings. A recent survey article reviewing outcomes from 31 studies found a median ICC of 0.01 (IQR 0 to 0.03). PASS 2008 was used for all sample size calculations.

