Data on whether the referral was made will be extracted in a multi-phase process that maximizes efficiency and accuracy. First, we will examine administrative data. FOBT codes are G0328, 82270, 82274, FOBT, FOBT1, FOBT2, FOBT3. We previously found that for 2,836 of 2,989 patients (95%) FOBT use identified by CPT code in the OPC was confirmed in the records of the local VA laboratory performing the test. Similarly, for 2,842 of 2,943 patients (97%) with an FOBT documented in the laboratory records, a CPT code was found in the OPC database. If administrative data reveal a CPT code for colonoscopy or FOBT, then patients will be considered to have undergone that test. If not, then we will examine orders. If no order exists, then we will examine laboratory reports and VISTA imaging. If no evidence of referral or screening is found at this point, then notes will be reviewed to determine whether participants refused, no-showed, received screening outside VA, or there is medical justification (e.g., life-limiting illness) for not receiving screening. The appropriate referral guideline will be based on the risk-categorization of the patient from their FHH. Patients will be coded as risk-appropriate referral or not; recommendation of any option listed as risk-appropriate will be classified as a risk-appropriate referral. Nonadherence to risk-appropriate referral could result from a referral being too aggressive based on risk categorization (e.g., a 40-year old without a FHH of CRC) or that the risk-appropriate referral was not made.

Patient uptake of CRC screening/surveillance recommendation will be evaluated as a secondary outcome. The patient uptake of CRC Screening/Surveillance referral will be examined for the subset of patients that received risk-appropriate referral by having an order in their record following the baseline visit for a CRC screening/surveillance referral. A binary variable will be created for each patient that was referred for CRC screening/surveillance (1=uptake of referred CRC screening, 0=no uptake of referred

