## Protocol: The Impact of Family History and Decision Support on High-Risk Cancer Screening

defined by performance of any of them. For the referral for genetic consultation outcome, all patients eligible for genetic consultation based on their risk profile from FHH will have their EMR audited to determine whether a risk-appropriate genetic consult referral was documented. A binary variable will be created for each patient (1=presence of risk-appropriate genetic consult referral, 0=absence) at 12-month follow up. A similar variable will be created to indicate whether participants received the recommended genetic consultation. As these secondary outcomes are binary, we will follow the same modeling strategy using GEE as described for the primary outcome. In exploratory analyses, similar outcomes will be created for the other cancer types (breast and ovarian) as described for CRC. We will calculate descriptive statistics for these outcomes and, if sample size is adequate, we will fit similar GEE as described for CRC.

The primary analyses for this cluster-randomized trial will be conducted on an intent-to-treat basis; participants will be analyzed in the group to which they were randomized, regardless of intervention adherence. Additional supporting analyses focusing on alternative, more restrictive analytic cohorts (e.g., per-protocol analysis) may be considered as exploratory analyses to provide additional information about the impact of amount of exposure to the intervention. Given that the outcomes will be determined based on EMR review over a 12-month period, there should be very little missing data. The most likely scenarios are that a participant dies during the study or leaves the VA system before completion of the 12-month follow-up period. However, we do not expect this to occur at a high rate; as needed, we will explore the impact with sensitivity analyses.

The main conclusions drawn from this trial will be based on the pre-specified primary and secondary hypotheses outlined previously and will be tested with two-sided p-values at the standard 0.05 level. For both primary and secondary outcomes, stratification variables (provider type and patient age categorization) will be included in GEE models. Statistical analyses will be performed using SAS for Windows (Version 9.2: SAS Institute, Cary, NC) and R (<http://www.R-project.org>).

### Aim 3

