## Protocol: The Impact of Family History and Decision Support on High-Risk Cancer Screening

being averted. As the short time frame of this study will not allow for the appropriate capture of such costs savings, we will rely on the literature to project long-term cost savings from averting CRC cases.

**Personnel Training and Quality Control.** Drs. [name] will train the PC and RA in standard survey and outcome assessment methods: 1) Careful scheduling and timely monitoring of the schedule to ensure that complete visits occur; 2) Collection of contact information at each visit; 3) Prompt contact and rescheduling of missed visits; 4) Review and documentation of the reasons for missed visits; and 5) Review and edit of participant data promptly to identify problems or missing values that can be completed by follow-up.

To decrease the risk of ascertainment bias and to standardize the abstraction, a detailed record abstraction protocol with data dictionary will be created, and training will be conducted by [name]. An electronic database will be developed for this purpose and will include quality measures such as mandatory fields and range checks. Quality will be further ensured by independent abstraction and data entry of 15% weekly by the study staff throughout the study, with comparison of the two abstractions and correction and retraining as needed.

**Safety Monitoring Plan.** Study staff will report any adverse event or unanticipated problem to the PI, [name] (gastroenterologist) immediately. These individuals will review all such events and determine the likelihood they were due to the study. The PI will report any serious, unexpected, and study-related adverse event or unanticipated problem to the local IRB according to the institution's requirements. The IRB will review all adverse events during continuing review, which will occur at least annually.

**Data Management, Storage, and Transfer.** Regarding privacy, research personnel will use only those parts of the medical record necessary to determine eligibility and follow the research protocol. Measures will be taken to maintain confidentiality during in-person sessions, such as scheduling them in a private room where other patients cannot overhear the conversation. All information security and privacy incidents will be reported to the ISO and PO immediately.

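### Staff who can see the arm abstract the primary outcome, its note-review step has no stated coding rule, and the planned safeguards standardise the work without masking it

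*Combined protocol and SAP*

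**What the plan says.** All references are to the combined protocol and SAP.

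- **Masking.** Under Procedures (both groups), research staff at Durham or Madison abstract the records. The text states that "Blinding cannot be ensured because the MeTree decision support document for PCPs will be scanned into CPRS" and adds that the research assistant cannot practically be kept from seeing it. No masked assessor is named for any outcome.
- **Primary outcome.** Under Analyses for Aims 1-2, each patient is scored 1 or 0 for risk-appropriate referral at 12 months. The MeTree algorithm sets the standard in both arms, and an appropriate referral before the baseline visit is taken into account.
- **Order of sources.** Administrative codes come first, then orders, then laboratory reports and imaging. If none of these shows a referral or a test, "notes will be reviewed to determine whether participants refused, no-showed, received screening outside VA, or there is medical justification". The text does not say which of these findings scores 1 and which scores 0.
- **Safeguards.** Personnel Training and Quality Control names ascertainment bias as a risk. It provides an abstraction protocol with data dictionary, training, mandatory fields and range checks. It then adds: "Quality will be further ensured by independent abstraction and data entry of 15% weekly by the study staff throughout the study".
- **Delayed arm.** Under Delayed (wait-list control) Condition, these patients' decision support document is uploaded by the same procedure, at about 12 months.

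**The concern.** The primary comparison is between arms, so an error in scoring does most harm when it differs by arm. Three features together allow that here. The abstractor can learn the arm. The cases left to the end depend on reading free text. The rule that turns that reading into a score is not written down. An abstractor who knows that a patient's PCP received a recommendation may read an ambiguous note as a referral more readily than the same note in the other arm.

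A second abstraction by study staff who can also see the arm measures consistency. Two readers with the same knowledge can agree and share the same lean. A larger sample would not help either, because the shift stays the same while the standard error shrinks.

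**Working it through.** **Inputs from the plan.** The test is described as "Based on a type I error rate of 5% and Z test for the difference of two proportions adjusted for provider clustering", and hypotheses are "tested with two-sided p-values at the standard 0.05 level". The target is "approximately 480 patients (240 in each arm) to detect a 13% difference (i.e., 73% in the immediate arm) with 80% power". The control rate is 60%, the ICC is 0.02, and there are 20 PCPs per arm, so 240/20 = 12 patients per PCP.

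**Step 1: reproduce the plan's figure.**
- Design effect = 1 + (12 − 1) × 0.02 = 1.22.
- Effective patients per arm = 240/1.22 = 196.7.
- The detectable difference at 80% power from 60% is 13.2 points (unpooled variance) or 13.3 (pooled). Table 1 gives 13.2, so the plan's figure is reproduced. With exactly 13 points the power is 78.2%, so the text has rounded.
- Inflation for loss: 480/0.96 = 500, as stated.

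**Step 2: standard error when the arms do not differ.** SE = sqrt(2 × 0.6 × 0.4 / 196.7) = 0.0494, or 4.9 points.

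**Step 3: shift from differential scoring.** Assume a true rate of 60% in both arms. Then 0.40 × 240 = 96 immediate-arm patients are truly non-adherent. Suppose a fraction b of them is credited with a referral in that arm only. The false difference is k = 0.40 × b, and the two-sided rejection rate is P(|Z + k/SE| > 1.96).

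| b (assumed) | Patients of 96 | Shift k | k/SE | Two-sided type I error |
|---|---|---|---|---|
| 0% | 0 | 0 points | 0 | 5% |
| 5% | about 5 | 2 points | 0.40 | 6.9% |
| 10% | about 10 | 4 points | 0.81 | 12.8% |

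Letting the variance change with the shifted rate gives 6.9% and 12.9%, so the approximation does not matter.

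**Step 4: what the plan can and cannot tell us about b.** The documents do not give b or the share of patients who reach note review. The 96 is an upper limit for miscrediting at that step under the 60% assumption. Some non-adherent patients are so because their referral was too aggressive; they have evidence of a referral and never reach the notes. If the same share were credited in both arms, the shift under no true effect would be zero. For scale, with the control arm at 60%, an observed difference of about 9.4 points is needed for significance. That is 0.094 × 240, or about 23 patients.

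**The case against.** The strongest reply is that the plan recognises the risk and already limits it. It names ascertainment bias and sets out a data dictionary, training, range checks and double abstraction. Notes are read only after codes, orders, laboratory and imaging records show nothing. Appropriateness follows one algorithm in both arms, and any listed option counts. All of this stands and narrows the room for judgement. None of it masks the arm or supplies the missing coding rule.

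It may also be said that the blinding sentence concerns the Aim 1 audit, which does not compare arms. That is where it stands, so applying it to the 12-month outcome is an inference. The inference is sound, because the stated reason is that the document is in the chart.

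A reader might infer more than the documents support:

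- *That the plan declares nothing can be done.* It says only that the research assistant cannot be kept from seeing the document.
- *That seeing the document reveals the arm.* Delayed-arm charts also receive one at about 12 months. In a chart read after that, its date shows the arm, not its presence.
- *That most of the scoring could be masked for free.* No share of patients settled before note review is given. The credit for earlier referral may also need record review, and a query and a scoring program take staff time.

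**Conclusion.** The point holds as a limited one. Abstraction of the primary outcome is unmasked, its final step is a reading of notes without a stated mapping to 1 or 0, and the planned safeguards do not hide the arm. The plan therefore leaves room for differential scoring that it could reduce.

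The 6.9% and 12.8% are illustrations. They rest on an assumed 5% or 10% miscrediting in the immediate arm only, a 60% true rate in both arms, an ICC of 0.02 and 12 patients per PCP. With no miscrediting the error rate is the nominal 5%. A reader might take these figures as evidence that the result is biased; the documents do not support that, since they say nothing about how often or in which direction staff would err. No design figure changes: 240 per arm and 500 in total remain. The change should be made because it protects the primary comparison at modest effort.

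**What to change.** 1. Obtain codes, orders, laboratory and imaging records by query where possible. Cover the 12 months after consent and also the pre-baseline look-back, whose length should be stated. A window of the 12 months alone would lose the credit that the outcome definition gives for earlier appropriate referral.
2. Have staff record only test, date and source. Assign the 1 or 0 by a program that uses those facts and the MeTree risk category and does not read arm.
3. Before abstraction starts, write down how each note finding is coded. For note-review cases, leave the study's MeTree note out of the material where feasible. Cross-site abstraction is optional: "Study staff at both sites (Durham and Madison) will have National Electronic Health Record (EHR) access", so it needs no new access, but it adds scheduling and gives limited masking.
4. Draw the existing 15% re-abstraction preferentially from note-review cases and report agreement by arm.

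The cost is an extraction query, a short scoring program and text for the abstraction manual, using existing staff and data. Masking remains incomplete for note-review cases, because PCP notes may themselves mention MeTree. That limitation should be reported with the results.

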## Analyses for Aims 1-2

**Sample Size and Power Considerations.** The CRC screening rate of patients aged 50 years and older in VA is high, around 80%. However, this is based on the assumption that all patients are average-risk; as such, the risk-appropriate referral rate is not well-characterized. We estimate that the risk-appropriate CRC screening referral rate is 60% to 70%. Our final sample size calculation is based conservatively on the screening referral rate of 60%. Based on a type I error rate of 5% and Z test for the difference of two proportions adjusted for provider clustering, we will need approximately 480 patients (240 in each arm) to detect a 13% difference (i.e., 73% in the immediate arm) with 80% power. Table 1 provides

estimated differences that can be detected with this sample size for different CRC screening referral rates. Lost to follow-up either due to death or the Veteran leaving the VA system will be minimal as outcome data are collected administratively. We inflated the sample size to 500 patients to account for a 4% loss to follow-up. Patients who screen as eligible but who never log in to complete MeTree either on their own or in person will not provide data for the study and thus will not be counted toward the required sample size of 500. Thus, we may screen and consent >500 patients in order to enroll 500 who complete MeTree.

By design, patients may not be independent because they are clustered within a participating provider. The “relatedness” of patients within a PCP is measured by the intraclass correlation coefficient (ICC) and must be considered in the sample size estimation. We have a fixed number of PCPs (20 in each arm). The sample size for difference in proportions is adjusted by the intraclass correlation coefficient (ICC); we used an ICC of 0.02. Although an ICC is difficult to estimate in advance of a study, we believe this is an appropriate and conservative estimate based on our own and others’ research findings. A recent survey article reviewing outcomes from 31 studies found a median ICC of 0.01 (IQR 0 to 0.03). PASS 2008 was used for all sample size calculations.

**The outcome for Aim 1 is rate of high-risk categorization.**

The analysis for this aim does not compare the outcome between arms as our aim is to determine if using MeTree to collect FHH improves the rate of high-risk identification for CRC compared to what is currently available administratively in VA. In our study design, both arms use MeTree to collect FHH, so the design for the aim is a pre-/post- comparison within Veterans. A binary variable will be created for each participant (1=presence of high-risk for CRC, 0=absence) at baseline (current practice) and following MeTree administration. We will test whether the rate of high-risk identification is higher following the MeTree administration compared to what is available in the medical record under current practice using a McNemar's test adjusted for PCP clustering. In addition to examining identification rates, specification of the source of identification of high-risk CRC will be important to formulating a standard identification strategy for clinical follow-up (e.g., referral to or receipt of colonoscopy screening).

**Table 2. Estimated differences in CRC screening/ surveillance uptake that can be detected between arms for different baseline screening/surveillance uptake with 80% power as well as different CRC screen referral rates**

Baseline referral rate for control arm	Sample size (control/ immediate )	Baseline screening/ surveillance uptake for control arm	Estimated difference between arms
60%	100/120	60%	18.0%
65%	100/120	65%	17.2%
70%	120/140	70%	15.0%

**The primary effectiveness outcome for Aim 2 is risk-appropriate CRC screening/surveillance referral for all patients, regardless of risk level.** Outcomes will be compared between arms to determine the impact of decision support on risk-appropriate referrals and screening/surveillance. The risk-appropriate screening/surveillance referral will be determined based on the MeTree algorithm. A binary variable will be created for each patient (1=adherent to risk-appropriate referral, 0=non-adherent to risk-appropriate referral) at 12-month follow up. The appropriateness of the referral will take into account if they were previously (prior to baseline visit) appropriately referred based on the current determination of their risk profile using the MeTree FHH data collection for both arms.

Data on whether the referral was made will be extracted in a multi-phase process that maximizes efficiency and accuracy. First, we will examine administrative data. FOBT codes are G0328, 82270, 82274, FOBT, FOBT1, FOBT2, FOBT3. We previously found that for 2,836 of 2,989 patients (95%) FOBT use identified by CPT code in the OPC was confirmed in the records of the local VA laboratory performing the test. Similarly, for 2,842 of 2,943 patients (97%) with an FOBT documented in the laboratory records, a CPT code was found in the OPC database. If administrative data reveal a CPT code for colonoscopy or FOBT, then patients will be considered to have undergone that test. If not, then we will examine orders. If no order exists, then we will examine laboratory reports and VISTA imaging. If no evidence of referral or screening is found at this point, then notes will be reviewed to determine whether participants refused, no-showed, received screening outside VA, or there is medical justification (e.g., life-limiting illness) for not receiving screening. The appropriate referral guideline will be based on the risk-categorization of the patient from their FHH. Patients will be coded as risk-appropriate referral or not; recommendation of any option listed as risk-appropriate will be classified as a risk-appropriate referral. Nonadherence to risk-appropriate referral could result from a referral being too aggressive based on risk categorization (e.g., a 40-year old without a FHH of CRC) or that the risk-appropriate referral was not made.

Patient uptake of CRC screening/surveillance recommendation will be evaluated as a secondary outcome. The patient uptake of CRC Screening/Surveillance referral will be examined for the subset of patients that received risk-appropriate referral by having an order in their record following the baseline visit for a CRC screening/surveillance referral. A binary variable will be created for each patient that was referred for CRC screening/surveillance (1=uptake of referred CRC screening, 0=no uptake of referred

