## Protocol: The Impact of Family History and Decision Support on High-Risk Cancer Screening

CRC screening) at 12-month follow up. Data on whether participants completed the CRC screening test will be obtained in a multi-step process. At the time of data abstraction, we will make a determination about whether to examine fee basis files for screens performed by non-VA providers according to whether the Durham and/or Madison VA is outsourcing CRC screening. Patients will be considered adherent if their medical record shows any risk-appropriate CRC test(s) performed in the time between completion of the computer program in clinic and 12-month follow-up.

Referral for genetic consultation will be examined as a secondary outcome. This outcome is risk-appropriate referral for genetic consultation or not. Because the Durham VAMC is online with GMS, a consult option will be generated to refer patients to GMS for genetic consultation, which may or may not include genetic testing. The Madison VAMC is not online with GMS. Therefore, fee basis files will be reviewed to determine if genetic counseling or testing was performed outside VA. The RA will review PCPs' consults and progress notes subsequent to the visit associated with completion of MeTree FHH regarding recommendations for genetic consultation. GI notes will also be reviewed to determine if a consult to GMS was made. Appropriate referral based on risk level will be classified as adherence. We will also examine the rate of receipt of a genetic consultation by conferring with GMS (which may be lower than the referral rate if the patient declines). As a relatively small proportion of participants are expected to receive genetic referral (6.4% in the Cone Health study), we will be underpowered to detect a significant effect. However, the descriptive rates will be informative from a policy perspective.

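### Orders are read only for patients with no colonoscopy or FOBT code, so the referral search can miss a risk-appropriate order and does not supply the order-based uptake denominator for coded completers

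*Combined protocol and SAP*

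**What the plan says.** All of this is under Analyses for Aims 1-2, in the text on the Aim 2 outcomes.

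- **Purpose of the search:** "Data on whether the referral was made will be extracted in a multi-phase process that maximizes efficiency and accuracy".
- **First stage:** "If administrative data reveal a CPT code for colonoscopy or FOBT, then patients will be considered to have undergone that test".
- **Next stages:** "If not, then we will examine orders. If no order exists, then we will examine laboratory reports and VISTA imaging". Notes are reviewed only if nothing has been found by then.
- **Scoring of the primary outcome:** "recommendation of any option listed as risk-appropriate will be classified as a risk-appropriate referral". The definition of the primary outcome also takes account of appropriate referrals made before the baseline visit.
- **Uptake denominator (secondary outcome):** patients who "received risk-appropriate referral by having an order in their record following the baseline visit for a CRC screening/surveillance referral".
- **Uptake numerator:** "Patients will be considered adherent if their medical record shows any risk-appropriate CRC test(s) performed in the time between completion of the computer program" and the 12-month follow-up. The text on completion data mentions several steps and possible use of fee basis files. It does not mention reading orders.

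Personnel Training and Quality Control promises a record abstraction protocol with a data dictionary. It is not part of the documents.

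**The concern.** The search is meant to answer a question about referrals, but a test code ends it. The two are not the same, and the difference matters for two outcomes.

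**(a) Primary outcome.** Take a patient whom MeTree classes as high risk. An FOBT is coded, the PCP also orders a colonoscopy, and no colonoscopy code appears by month 12. The FOBT code settles the patient's status and the colonoscopy order is not read. If FOBT is not an accepted option for that risk class, the patient is scored non-adherent although a risk-appropriate referral was made. FOBT codes are plausible in this population, because eligibility excludes recent endoscopy.

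**(b) Uptake.** The denominator is defined by a post-baseline order. Patients with a completed-test code are those whose orders the search does not reach, so it yields neither an order nor an order date for them. Someone would have to decide during abstraction or analysis how to place them. The plan concedes that blinding of record abstraction cannot be ensured, so that choice should be fixed in advance.

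**Working it through.** **The plan's own figures reproduce.** The check uses a two-sided 5% test and an ICC of 0.02.

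- Primary outcome: 240 per arm over 20 PCPs gives 12 patients per PCP and a design effect of 1 + 11 × 0.02 = 1.22. The detectable difference from 60% is 13.3 points with pooled variance and 13.2 unpooled (Table 1: 13.2).
- Uptake: 100 and 120 patients over 20 PCPs each give design effects of 1 + 4 × 0.02 = 1.08 and 1 + 5 × 0.02 = 1.10. The detectable difference from 60% is 18.1 points (Table 2: 18.0).

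The issue is the extraction rule, not the power arithmetic.

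**Part (a): possible size.** Let H be the high-risk share, F the share of those with an FOBT code, c the colonoscopy order rate among them in the control arm, and c + 0.30 the rate in the immediate arm. Let u be the share of orders unfilled. The documents give none of H, F, c or the 0.30. Assume H = 0.10 to 0.25 and F = 0.20 to 0.40, equal in both arms and independent of ordering, so H × F = 0.02 to 0.10. Assume also that FOBT is not an option for the class.

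Change in the arm difference = H × F × [(c + 0.30) × u(immediate) − c × u(control)]. A positive value means the difference is understated.

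| Unfilled share | Bracket | Change overall |
|---|---|---|
| 40% in both arms (from 60% uptake) | 0.30 × 0.40 = 0.12, for any c | 0.24 to 1.2 points understated |
| 22% immediate, 40% control (from 78% and 60% uptake), c = 0 | 0.066 | 0.13 to 0.66 points understated |
| As above, c = 0.37 | 0.066 − 0.18 × 0.37 ≈ 0 | none |
| As above, c = 0.70 | 0.066 − 0.126 = −0.060 | 0.12 to 0.60 points overstated |

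The plan's 60% uptake is its control-arm figure. Its detectable alternative for the immediate arm is 60 + 18 = 78%, so the lower rows fit its planning assumptions better. There the sign turns at c = 0.066 / 0.18 ≈ 0.37.

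**Part (b): what the search delivers.** Use Table 2's first row (100 control, 120 immediate) with uptake of 60% and 78%.

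- Completers: 100 × 0.60 = 60 and 120 × 0.78 ≈ 94.
- Non-completers: 40 and about 26.
- The plan reports a code for 2,842 of 2,943 laboratory FOBTs, so 101 / 2,943 = 3.4% had none. If that share held for all tests, about 2 of 60 and 3 of 94 completers would reach the order stage. Orders would then be read for about 42 of 100 and 30 of 120 patients.

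Most of the intended denominator would therefore have no order information from this search. Flexible sigmoidoscopies and fee-basis tests without a colonoscopy or FOBT code would add some back.

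One obvious patch is to treat every code as an order. Suppose x patients in an arm had a test that was ordered before baseline but done in the window. They enter as successes only, so control uptake becomes (60 + x) / (100 + x), which exceeds 60% for any x > 0. A patient whose pre-baseline order went unfilled has no code and is not added, so the patch inflates uptake by an amount that may differ between arms.

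**The case against.** **The uptake paragraph stands on its own.** It defines its subset by orders, so anyone applying it must look orders up. The cascade serves the referral outcome only. This is fair, and it rules out a reading that a reader might reach: that measured uptake would fall close to zero because only non-completers have orders on file. That would require abstractors to ignore the uptake definition. What stands is that the only search described does not collect those orders, and no other section says how they are obtained.

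**The search does not stop at the first code.** Administrative data are reviewed as a stage, so a colonoscopy code beside an FOBT code would be seen. This stands, and part (a) is limited to patients with no colonoscopy code. The rule might even be read test by test, with colonoscopy orders still checked when only an FOBT is coded. That would cure (a) but not (b), because the order behind the coded test would remain unread.

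**Part (a) rests on an unstated premise.** The documents list no screening options by risk class. Colonoscopy appears only as an example of follow-up for high-risk patients in the Aim 1 text. The premise cannot be verified and must stay a condition.

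**Bias toward no effect is tempting but not shown.** Decision support reaches only the immediate arm within 12 months, so one may infer that missed orders concentrate there. Orders are missed only when unfilled, however, and the plan's alternative has fewer unfilled orders in that arm. Control losses count too, and the sign can reverse.

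**The abstraction protocol may already cover this.** It may, but it would then depart from the written rule, which would still need amending.

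**Conclusion.** The concern holds as a defect in the written extraction rule. Part (b) is the firmer half: it needs no assumed rates, only the mismatch between an order-based denominator and a search that omits orders for patients with a test code. The orders do exist in the record, so the denominator is recoverable. The plan simply does not say that it will be recovered.

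Part (a) is real but conditional and probably small. Under the assumptions above, the primary difference of 13 points would move by about 1 point or less in most cases, from 1.2 points understated to 0.6 points overstated. A reader could construct a much larger loss. With 20% of patients high risk, 30% of those affected, and the error confined to the immediate arm, 0.20 × 0.30 × 73% = 4.4 points are lost and power drops from 78% to 43%. The documents do not support this. Both shares are assumed, and it needs no missed order at all among controls. With the same shares in both arms the difference falls only to 12.2 points and power to 71%.

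The rule should be amended. The planned sample size is not affected.

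**What to change.** Amend the extraction text under Analyses for Aims 1-2, and the abstraction protocol to match:

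1. Read CRC orders, with type and date, for every patient, whatever test codes are found.
2. Score the primary outcome on any referral that matches the patient's risk class. Keep the look-back before the baseline visit, since the outcome definition credits earlier appropriate referrals; a window that opened only at consent would misclassify those patients.
3. Define the uptake set from orders dated after the baseline visit, and link each completed test to its order.
4. Keep note review for patients with no evidence in any source.
5. State which options count as risk-appropriate for each risk class under the MeTree algorithm, so that the scoring can be checked.

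The cost is an order look-up for patients who already have a test code, done by staff who already open these records.
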